- 12. Has a heart rate <50 beats per minute. If bradycardia is secondary to iatrogenic or treatable causes and these causes are treated, a heart rate assessment can be repeated during the screening period.
- 13. Has a clinically significant CNS abnormality that is most likely contributing to the dementia or findings on MRI or CT including:
 - a. intracranial mass lesion (including but not limited to meningioma [>1 cm³ with evidence of peritumoral edema] or glioma)
 - b. vascular malformation

- c. intracranial aneurysm >4 points by PHASES score (Appendix L)
- d. evidence of >4 hemosiderin deposits (definite microhemorrhage or superficial siderosis)
- 14. Has clinically significant neuroimaging or laboratory abnormalities during Screening that in the judgment of the Investigator would jeopardize the safe participation of the subject in the study. In consultation with the Medical Monitor, these subjects may be rescreened after appropriate treatment of their medical condition.
- 15. Has major surgery planned during the screening through end of the treatment or follow-up periods
- 16. Requires treatment with a medication or other substance that is prohibited by the protocol
- 17. Has a body mass index (BMI) $<18.5 \text{ kg/m}^2$ or known unintentional clinically significant weight loss (i.e., $\ge 7\%$) over past 6 months
- 18. The urine drug screen result at Visit 1 (Screening) indicates the presence of amphetamine/methamphetamine, barbiturates, cocaine, or phencyclidine (PCP). Subjects who test positive for amphetamines may be retested during Screening if they agree to abstain from the medication for the length of their participation in the study and if abstinence from medication usage is achieved at least 7 days prior to Visit 2 (Baseline). The repeat Screening test must be negative for them to participate in the study. The presence of benzodiazepines, marijuana (THC), or opiates does not necessarily exclude the subject from the study.
- 19. Is suicidal at Screening or Baseline as defined below:
 - a. If the subject can complete the Columbia Suicide Severity Rating Scale (C-SSRS), he or she must not be actively suicidal at Visit 1 (Screening) or Visit 2 (Baseline) (including, an answer of "yes" to C-SSRS questions 4 or 5 [current or over the last 6 months]) and must not have attempted suicide in the 2 years prior to Visit 1 (Screening); OR

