 - b. If the subject is not able to reliably complete the C-SSRS in the Investigator's judgment, the subject must not be suicidal as assessed by the Global Clinician Assessment of Suicidality (GCAS) score (i.e., a score of 3 or 4) based on Investigator's assessment of behavior within the 3 months prior to Visit 1 (Screening) or since-last-visit at Visit 2 (Baseline); OR
 - c. The subject is actively suicidal in the Investigator's judgment

20. Has participated in or is participating in a clinical trial of any investigational drug, device, or intervention, within 30 days or 5 half-lives, whichever is longer, of Visit 2 (Baseline)

- 21. Has previously been enrolled in any prior clinical study with pimavanserin or is currently taking pimavanserin.
- 22. Has a significant sensitivity or allergic reaction to pimavanserin or its excipients
- 23. Is an employee or is a family member of an employee of Acadia Pharmaceuticals Inc.
- 24. Is judged by the Investigator or the Medical Monitor to be inappropriate for the study for any reason, including if the subject is judged to be a danger to self or others

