4.4 Subject Withdrawal or Termination

In accordance with the Declaration of Helsinki and other applicable regulations, a subject has the right to withdraw from the study at any time, and for any reason, without prejudice to his or her future medical care.

If consent has been given by a legally acceptable representative (LAR) because the subject is not competent to provide informed consent, the LAR has the right to withdraw the subject from the study at any time, and for any reason, without prejudice to the subject's future medical care or any penalty or loss of benefits to the LAR.

Subjects may be discontinued or withdrawn from the study for a number of reasons, including, but not limited to, those listed below:

- Adverse event
- Death
- Lack of efficacy
- Lost to follow-up
- Non-compliance with study drug
- Use of prohibited medication
- Physician decision
- Pregnancy
- Protocol deviation
- Study terminated by Sponsor
- Subject or LAR withdraws consent
- Other

If at any time the C-SSRS or GCAS results for a given subject reveal potential suicidality, then the Investigator should assess the clinical significance of such results. If a clinically

significant risk of suicidality is identified for a subject, then the Investigator should discontinue the subject and implement appropriate treatment (Sections 6.3.5 and 6.3.6).

Every reasonable effort should be made to complete Visit 7/ET and the safety follow-up period if a subject discontinues from the study for any reason.

If a subject is lost to follow-up, every reasonable effort should be made to phone the subject approximately 4 weeks after last known contact with the subject in order to assess the subject's current status. All phone contact with the subject should be documented.

For subjects who continue to be followed for safety, SAEs should continue to be reported as described in Section 7.4.2.

If a subject is discontinued from the study because of an AE, every reasonable attempt should be made to follow the subject until the AE resolves or until the Investigator deems the AE to be chronic or stable.

All SAEs will continue to be followed until such events have resolved or the Investigator deems them to be chronic or stable.

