
6.1.2 **Mini-Mental State Examination**

The MMSE is a brief 30-point questionnaire that is used to quantitatively assess cognition (Folstein et al. 1975). The MMSE includes simple questions and problems in a number of areas: the time and place of testing, repeating lists of words, arithmetic, language use and comprehension, and copying a drawing. The MMSE is being used in this study to screen for cognitive impairment and as a safety measure.

The MMSE will be assessed at all scheduled visits.

6.1.3 **Medical History and Demographics**

A complete medical history will be obtained from each potential subject. Demographic information, including date of birth, gender, race, and ethnicity will be recorded as well. Any new medical condition beginning after the informed consent form (ICF) has been signed will

be captured as an AE. Subjects may be asked to provide pharmacy or medical records to substantiate the medication history.

6.1.4 **Psychiatric History**

Details of the subject's psychiatric history and treatment will be collected.

6.1.5 **Dementia History**

Details of the subject's dementia diagnosis and treatment will be collected, including the date that dementia was determined.

6.1.6 **Neurological History**

Details of the subject's neurological diagnosis and treatment will be collected, including the date that any neurological disease was determined.

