6.3.5 Columbia-Suicide Severity Rating Scale

The C-SSRS monitors changes in suicidal thinking and behavior over time, in order to determine risk (Posner et al. 2011). The following four constructs are measured: the severity of ideation, the intensity of ideation, behavior, and lethality.

The C-SSRS will be used to assess suicidal ideations and behaviors in subjects who are able to complete the assessment (subjects without dementia, defined as an MMSE ≥25, and subjects with dementia who the Investigator has determined can complete the C-SSRS). Whether or not the subject can complete the C-SSRS should be documented for each subject.

For subjects who are able to complete the assessment, the Baseline/Screening version will be administered at Visit 1 (Screening), and the Since Last Visit version will be administered at subsequent visits. The C-SSRS results for each subject should be reviewed by the Investigator at each visit. If at any time the C-SSRS results for a given subject reveal potential suicidality, then the Investigator should assess the clinical significance of such results. If a clinically significant risk of suicidality is identified for a subject, then the Investigator should discontinue the subject and implement appropriate treatment (Section 4.4).

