6.3.6 Global Clinician Assessment of Suicidality

The GCAS is a clinician-rated, 5-point scale that is designed to rate the subject's suicidality based on the report of the subject, the report of the study partner/caregiver, and the clinician's

Final Version: 1.0 Date: 5 March 2021

Final Version: 1.0 Date: 5 March 2021 Clinical Study Protocol Amendment 7

global assessment. Ratings can be 0 ("Absent"), 1 ("Feels life is not worth living"), 2 ("Wishes he/she were dead or any thoughts of possible death to self"), 3 ("Suicidal ideas or gesture"), or 4 ("Attempt at suicide"). The Investigator will record a subject rating, a study partner/caregiver rating, and a clinician rating.

If the subject is not able to reliably complete the C-SSRS in the Investigator's judgment, the GCAS will be administered and used thereafter in the study. If the GCAS is administered, at Visit 1 (Screening) lifetime suicidality and suicidality for the past 3 months will be assessed and at all other visits, suicidality since the previous visit will be assessed.

As with the C-SSRS, if at any time the GCAS results for a given subject reveal potential suicidality, then the Investigator should assess the clinical significance of such results. If a clinically significant risk of suicidality is identified for a subject, then the Investigator should discontinue the subject and implement appropriate treatment (Section 4.4).

6.3.7 **Extrapyramidal Symptom Rating Scale-Abbreviated**

The ESRS (Chouinard and Margolese 2005) was developed to assess drug induced movement disorders such as parkinsonism, akathisia, dystonia and tardive dyskinesia with established reliability, validity, and sensitivity. It consists of a questionnaire of parkinsonian symptoms, physician examination of parkinsonism, dyskinetic movements, and global impression of tardive dyskinesia. The ESRS-A, an accepted modified form of the original ESRS, will be used during the study to monitor for any worsening in extrapyramidal symptoms or signs at scheduled and unscheduled visits.

6.3.8 **Laboratory Evaluations**

Clinical labs (including HbA1c at screening only) are encouraged, but not required to be completed under fasting conditions. The laboratory evaluations will include, but are not be limited to, the following:

- Clinical chemistry serum tests
 - o Sodium (Na), potassium (K), chloride (Cl), phosphorus (P), calcium (Ca), magnesium (Mg), carbon dioxide (CO₂), blood urea nitrogen (BUN), creatinine (CR), uric acid

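### The fixed 2-year suicide-attempt exclusion covers only subjects who can complete the C-SSRS; for GCAS subjects an attempt more than 3 and up to 24 months before Visit 1 is excluded only by judgment

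*Protocol*

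**What the plan says.** Exclusion 19 in Protocol Section 4.3 has three limbs, and the synopsis repeats them.

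- **19a** opens with the condition that the subject can complete the C-SSRS. Such a subject must not be actively suicidal, and a yes to question 4 or 5, now or in the preceding 6 months, counts as such. The second requirement in this limb reads: "must not have attempted suicide in the 2 years prior to Visit 1 (Screening); OR".
- **19b** applies when the subject cannot reliably complete the C-SSRS. It excludes a GCAS score of 3 or 4, resting on the Investigator's "assessment of behavior within the 3 months prior to Visit 1 (Screening") or, at Visit 2, on the period since the last visit.
- **19c** applies to everyone: "The subject is actively suicidal in the Investigator's judgment".

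Exclusion 24 also applies to everyone: "Is judged by the Investigator or the Medical Monitor to be inappropriate for the study for any reason". It goes on to name subjects thought to be a danger to themselves or to other people.

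Protocol Section 6.3.5 gives the C-SSRS to subjects without dementia (MMSE of 25 or more) and to "subjects with dementia who the Investigator has determined can complete the C-SSRS". The rest receive the GCAS. Under Section 6.3.6, "at Visit 1 (Screening) lifetime suicidality and suicidality for the past 3 months will be assessed", and a rating of 4 denotes a suicide attempt. Section 4.4 adds an instruction that begins "If at any time the C-SSRS or GCAS results for a given subject reveal potential suicidality": the Investigator is to assess clinical significance and discontinue the subject if the risk is clinically significant. Under Section 6.1.4, details of the subject's "psychiatric history and treatment will be collected".

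**The concern.** The protocol treats a suicide attempt within 2 years as serious enough for an automatic bar, but writes that bar inside a condition about which scale the subject can complete. Two subjects who each attempted suicide 12 months before Visit 1 are handled differently: the one on the C-SSRS is out by rule, and the one on the GCAS depends on judgment. For subjects with dementia, the Investigator also decides which scale applies.

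The GCAS route is a real one. Inclusion 5 admits an MMSE as low as 6, and depression/dysphoria is one of the qualifying NPI domains in inclusion 6, so suicide history matters in this population. What is at stake is patient safety at entry and even application of a stated rule.

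**Working it through.** This is a reading of the text plus one subtraction. The plan states no figure to reproduce on this point.

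**Step 1: does the 2-year clause reach GCAS subjects?** It is part of the sentence governed by the opening condition of 19a. 19b is a separate limb for the complementary group and has its own window. So the clause does not carry over.

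**Step 2: is there an attempt window for GCAS subjects elsewhere?**

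| Provision | Who | Attempt look-back | Type |
|---|---|---|---|
| 19a | Can complete C-SSRS | 24 months before Visit 1 | Fixed |
| 19b (GCAS 4 = attempt) | Cannot reliably complete C-SSRS | 3 months before Visit 1, or since last visit at Visit 2 | Fixed |
| 19c | All | None; present state | Judgment |
| 24 | All | None; names danger to self | Judgment |
| Sections 4.4 and 6.3.6 | GCAS subjects (parallel rule for C-SSRS) | None; clinically significant risk | Judgment |

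The synopsis has the same structure. SAP Sections 5.2.6, 5.2.7 and 8.2 describe assessment and tabulation periods and add no eligibility rule.

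**Step 3: size of the gap.** 2 years = 24 months, and 24 − 3 = 21 months. This is a length of look-back, not a share of subjects or of risk.

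**Step 4: would the attempt come to light?** An attempt 12 months before Visit 1 should give a lifetime GCAS rating of 4 at Visit 1. No fixed eligibility criterion uses that lifetime rating. It does not date the attempt. Psychiatric and medical history may, and SAP Section 9 lists medical-history start and stop dates when available.

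**Step 5: number affected.** Number = enrolled × share on the GCAS route × share of those with an attempt more than 3 and up to 24 months before Visit 1. Planned enrollment is about 750. The documents give neither of the other two terms, so no count can be calculated.

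**The case against.** The strongest reply is that protection exists and only an automatic rule is missing. The lifetime GCAS asks about the attempt before randomization, with subject, caregiver and clinician ratings recorded. The Investigator must then weigh any potential suicidality. Exclusion 24 names danger to oneself and can be invoked by the Medical Monitor as well as the Investigator. All of this stands, and it is why the point is minor. It does not remove the inconsistency: the general judgment safeguards cover C-SSRS subjects too, yet a fixed 2-year rule was still written for them. Protocol Section 10.6 allows no eligibility waivers, so a fixed criterion differs in practice from a judgment.

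A second reply is that scale-specific windows may be deliberate, since 3 months matches the recent period the GCAS rates. The documents state no such rationale. It would fit ideation better than attempts, because an attempt is a discrete event that a caregiver or record can report.

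A third reply is that dating an attempt is hard in these subjects. That stands in part. Inclusion 9 sets no minimum length of acquaintance for the caregiver, and some dates will be unobtainable, so the fix needs a rule for them. The difficulty may not be peculiar to the GCAS route, however: the C-SSRS baseline periods tabulated in SAP Section 8.2 are 6 months and lifetime, which do not mark 24 months either.

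A reader might infer more than the text supports:

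- *GCAS subjects with an attempt in the gap are unprotected, or are admitted as a matter of course.* The three judgment provisions contradict this.
- *19b is looser throughout.* Within its 3 months it bars GCAS 3 (ideas or gesture), whereas 19a names only C-SSRS questions 4 and 5 on ideation, over a longer window.
- *The treatment comparison is biased.* Eligibility is settled before randomization and applies alike to both groups.

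**Conclusion.** The inconsistency is real and minor. The fixed attempt exclusion reaches back 24 months on the C-SSRS route and 3 months on the GCAS route. In the 21 months between, a GCAS subject's attempt is excluded only by judgment, although the Visit 1 lifetime rating should flag it. No estimate or test in the SAP is affected. That few subjects are involved is a judgment, not a calculation.

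The conclusion assumes that the criteria as given apply everywhere. The country-specific amendments for the Czech Republic and Bulgaria are only summarized in SAP Section 1, and the summary mentions no suicidality criterion.

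**What to change.** Take the 2-year attempt clause out of 19a and make it a separate sub-item of exclusion 19 that applies to every subject whichever scale is used. Make the same change in the synopsis. Leave the ideation thresholds and windows in 19a and 19b as they are.

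For a lifetime GCAS rating of 4 at Visit 1, date the last attempt from the subject, the caregiver, or the psychiatric and medical history already collected. If it cannot be shown to lie more than 2 years before Visit 1, either exclude the subject or require documented Medical Monitor review before randomization.

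The cost is one moved clause and a date check, with no new instrument or visit, and a few more screen failures. The change cannot reach subjects already enrolled: SAP Section 16.2 puts 288 subjects in the December 2019 interim lock, before the March 2021 date of Amendment 7. SAP version 4.0, of May 2022, already plans for database lock. If enrollment has closed, which the documents do not state, the value lies in later protocols that reuse this wording.

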4.4 Subject Withdrawal or Termination

In accordance with the Declaration of Helsinki and other applicable regulations, a subject has the right to withdraw from the study at any time, and for any reason, without prejudice to his or her future medical care.

If consent has been given by a legally acceptable representative (LAR) because the subject is not competent to provide informed consent, the LAR has the right to withdraw the subject from the study at any time, and for any reason, without prejudice to the subject's future medical care or any penalty or loss of benefits to the LAR.

Subjects may be discontinued or withdrawn from the study for a number of reasons, including, but not limited to, those listed below:

- Adverse event
- Death
- Lack of efficacy
- Lost to follow-up
- Non-compliance with study drug
- Use of prohibited medication
- Physician decision
- Pregnancy
- Protocol deviation
- Study terminated by Sponsor
- Subject or LAR withdraws consent
- Other

If at any time the C-SSRS or GCAS results for a given subject reveal potential suicidality, then the Investigator should assess the clinical significance of such results. If a clinically

significant risk of suicidality is identified for a subject, then the Investigator should discontinue the subject and implement appropriate treatment (Sections 6.3.5 and 6.3.6).

Every reasonable effort should be made to complete Visit 7/ET and the safety follow-up period if a subject discontinues from the study for any reason.

If a subject is lost to follow-up, every reasonable effort should be made to phone the subject approximately 4 weeks after last known contact with the subject in order to assess the subject's current status. All phone contact with the subject should be documented.

For subjects who continue to be followed for safety, SAEs should continue to be reported as described in Section 7.4.2.

If a subject is discontinued from the study because of an AE, every reasonable attempt should be made to follow the subject until the AE resolves or until the Investigator deems the AE to be chronic or stable.

All SAEs will continue to be followed until such events have resolved or the Investigator deems them to be chronic or stable.

Should a subject request or decide to withdraw, every reasonable effort will be made to complete and report observations as thoroughly as possible up to the date of withdrawal, including the evaluations specified at the ET visit outlined in Table S-1. Unless the subject has withdrawn consent to be contacted for this study, every reasonable effort will be made to complete the 30-day safety follow-up telephone call for all subjects who withdraw prematurely. All information will be reported on the applicable pages of the electronic case report form (eCRF).

The Sponsor reserves the right to discontinue the study at any time for any reason. Such reasons may be any of, but not limited to, the following:

- Occurrence of AEs unknown to date in respect of their nature, severity, and duration or the unexpected incidence of known AEs
- Medical, ethical, or business reasons affecting the continued performance of the study Regulatory authorities also have the right to terminate the conduct of the study in their region for any reason.

4.5 **Prior and Concomitant Therapy**

4.5.1 **Prior Medications**

Prior medications are defined as any medication taken before the date of the first dose of study drug.

Study: ACP-103-046 Clinical Study Protocol Amendment 7

4.5.2 Concomitant Medications

Concomitant medications are defined as any medication taken on or after the date of the first dose of study drug.

In order to ensure that appropriate concomitant therapy is administered, it is essential that subjects be instructed not to take any medication without prior consultation with the Investigator (unless the subject is receiving treatment for a medical emergency).

4.5.2.1 Permitted, Restricted, and Prohibited Medications

Prohibitions and restrictions for concomitant medications should be followed between the initial screening visit and Visit 7/ET as specified in Appendix H and Appendix I. These appendices do not constitute an exhaustive list and any questions regarding prohibited and restricted medications should be discussed with the Medical Monitor or designee.

Use of medications that could interfere with study conduct or any questions regarding prohibited and restricted concomitant medications should be reviewed and/or discussed with the Medical Monitor or designee.

Medications that can prolong QT interval are prohibited (or restricted if approved by the Medical Monitor, or appropriate designee) as specified in Appendix H.

If a subject is on a medication restricted by the protocol, the medication should be adjusted only if it is determined by the Investigator to be clinically appropriate (e.g., if the subject's symptoms are not well-controlled or if the subject cannot tolerate the current medication) in consultation with the treating physician.

The Investigator may prescribe, adjust, or discontinue appropriate medication to treat or manage AEs. Subjects who require current treatment with a prohibited medication will be withdrawn from the study.

Subjects who have previously taken a prohibited medication during the study will be withdrawn from the study unless:

- the prohibited medication has been discontinued AND
- withdrawal from the study presents an unacceptable medical risk to the subject

The justification to allow the subject to continue in the trial will be made by the Sponsor/Medical Monitor, with medical input from the Investigator, and will be documented. If a subject is allowed to remain in the trial, this will be reported as a major protocol deviation and not a waiver.

Final Version: 1.0

Date: 5 March 2021

Permitted concomitant medications should remain at a stable dose throughout the study. Benzodiazepines (lorazepam up to 1 mg/day or equivalent) are allowed as rescue medication as needed for severe neuropsychiatric or behavioral disturbances (Appendix H).

